3. ANALYSIS SETS

3.1. Definition of Analysis Sets

Data analyses will be based on the four analysis sets defined below. Analysis sets, including exclusions based on key deviations, will be reviewed and approved by G1 Therapeutics prior to the study unblinding.

3.1.1. Intent-to-Treat Analysis Set

The intent-to-treat (ITT) analysis set includes all randomized patients. Analyses using the ITT will be conducted on the basis of the assigned treatment. The ITT is the primary analysis set for all efficacy analysis.

3.1.2. Modified ITT Analysis Set

A modified ITT (mITT) analysis set is a subset of the ITT analysis set and will only include the ITT patients who received at least 1 dose of study drug (etoposide, carboplatin, atezolizumab, or trilaciclib). Supportive sensitivity analyses will be conducted on the mITT analysis set for primary and key secondary efficacy endpoints to evaluate the robustness of the results. Analyses using the mITT will be conducted on the basis of the assigned treatment.

3.1.3. Safety Analysis Set

The safety analysis set includes all enrolled patients who received at least 1 dose of study drug (etoposide, carboplatin, atezolizumab, or trilaciclib). Analyses using the safety analysis set will be conducted on the basis of the actual treatment received. All safety analyses will be assessed using the safety analysis set.

3.1.4. Per Protocol (PP) Analysis Set

The per-protocol (PP) analysis set is a subset of the mITT analysis set and may also be used to analyze select endpoints. The criteria for inclusion in the PP analysis set will be based on study drug administration and major protocol deviations, and it will be finalized and documented prior to unblinding patients in the study.

It will include only those patients who have no key protocol deviations (as described in [Section 3.2](#)) and who received the treatment to which they were randomized. For any patients who received the wrong treatment during any part of the study, their data will be excluded from the PP analysis set. PP analysis set may be used to analyze selected endpoints to test the robustness of results.

3.1.5. Response Evaluable Analysis Set

The Response Evaluable Analysis Set will include all patients who are in the mITT and (1) have at least 1 post-baseline tumor assessment, (2) discontinued treatment because of clinical progression, or (3) died due to disease progression before their first postbaseline tumor scan. The response evaluable analysis set will be used for analyses of tumor response.

3.1.6. Pharmacokinetics (PK) Analysis Set

The PK Analysis Set will not be used for any analyses described in this SAP. Rather the PK analyses and the PK Analysis Set will be described in a separate document.

3.2. Protocol Deviations

Certain protocol deviations are key in that they may affect the ability to assess the safety and efficacy of study drug. Patients with key deviations will be excluded from the PP analysis set. All patients who meet the definition of the ITT/mITT analysis sets will be included in the ITT/mITT analysis set regardless of these deviations.

The criteria for inclusion in the PP set will be finalized and documented prior to unblinding patients for the study.

If a patient is randomized, but fails to receive treatment, the reason for not receiving treatment will be noted in the CSR. Any such patients who are not treated will be excluded from the mITT, safety, response evaluable, and PP analysis sets but will be included in the ITT and in the patient listings for the CSR.

If the wrong treatment is administered to a patient, and the reason for the incorrect treatment is documented, this will be noted in the CSR and the patient's data included in the Safety Analysis Set based on the actual treatment received. All major protocol deviations will be reviewed in a data review meeting to classify protocol deviations as non-key or key, and to discuss the potential impact on statistical analysis. This will be documented in a note to file prior to database lock and unblinding.

4. PROSPECTIVELY DEFINED ANALYSES

As outlined in the protocol, trilaciclib is an IV cyclin dependent kinase (CDK) 4/6 inhibitor being evaluated for its ability to decrease chemotherapy-induced myelosuppression when administered in combination with cytotoxic chemotherapy. Unlike granulocyte-colony stimulating factor (GCSF), which stimulates production of neutrophils, and transfusions, which only replace red blood cell (RBC) or platelets, trilaciclib is hypothesized to facilitate myelopreservation of all hematopoietic lineages including neutrophils, RBC, platelets, lymphocytes, etc.

To capture the potential for multilineage trilaciclib benefit, the following analyses are prospectively proposed in Table 3 and their associated endpoint derivation and analysis methods will be detailed in Sections 5.1 and 6.2.7 with the multiplicity adjustments described in Section 6.2.7.1.4.

Table 3 Prospectively Defined Analyses

Occurrence (proportion of patients) of severe (Grade 4) neutropenia
Duration of severe (Grade 4) neutropenia in Cycle 1
Occurrence (proportion of patients) of RBC transfusions on/after 5 weeks
Occurrence (proportion of patients) of GCSF administration
Cumulative incidence of major adverse hematologic events (MAHE) which is defined to include components as the following: 
 • All-cause hospitalizations • All-cause dose reductions • Febrile neutropenia • RBC transfusions on/after 5 weeks • Prolonged severe (Grade 4) neutropenia (duration > 5 days)
All-cause hospitalizations in the MAHE composite
All-cause dose reductions in the MAHE composite
Febrile neutropenia in the MAHE composite
RBC transfusions on/after 5 weeks in the MAHE composite
Prolonged severe (Grade 4) neutropenia in the MAHE composite

RBC = Red Blood Cell; GCSF = granulocyte-colony stimulating factor;

5. PRIMARY AND SECONDARY ENDPOINTS

The following general definitions will be applied to all endpoints derivation unless otherwise specified.

Term	Definition
Severe Neutropenia (SVN)	ANC lab value that meets the common terminology criteria for adverse events (CTCAE) criteria for \geq Grade 4 toxicity
Cycle baseline	The last non-missing value within the window starting from 3 days prior to the date/time of study drug administration on Day 1 of Cycle 1 and 1 day prior to Day 1 of each subsequent cycle (i.e. Cycle 2, Cycle 3, etc.); must be prior to the time of study drug administration
Cycle nadir	The lowest value for a given hematologic parameter that occurs between start of cycle and end of cycle and is less than the cycle baseline.
Duration of cycle	Total number of days from start of cycle to end of cycle, that is, date of end of a cycle - date of start of cycle + 1.
End of cycle*	Day 1 of the subsequent cycle. For example, the end of cycle for Cycle 1 is Day 1 of Cycle 2. For the last induction cycle (where no subsequent maintenance cycle is given), the end of cycle will be defined as Day 36 after the first dose of the cycle. For the last maintenance cycle, the end of cycle will be defined as Day 30 after the first dose of the cycle.
Start of cycle	Day 1 of each cycle starts with the administration of study drug(s) (etoposide, carboplatin, atezolizumab, or trilaciclib)
Start of study	Date of randomization
Study baseline	The last non-missing value prior to, or on the date of administration of study drug(s) (etoposide, carboplatin, atezolizumab, or trilaciclib); must be prior to the time of study drug administration
Change from baseline	Calculated as the post-baseline value minus the baseline value. If the baseline value is missing for a particular endpoint, change from baseline will be missing.
Induction treatment period	Between the date of randomization and end of cycle for the last Induction cycle.
Maintenance treatment period	Between the date of Day 1 of the first maintenance cycle and end of cycle for the last Maintenance cycle.
Overall treatment period	Between the date of randomization and end of cycle for the last cycle.

* For various hematologic parameter analyses, the last assessment prior to end of cycle will be utilized in the analyses. Situations where this applies will be indicated as such.

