Time to first occurrence of a MAHE will be used as a sensitivity analysis in support of the total number of MAHE. It is defined as the first time to observe an event among all the components, starting from the date of randomization. Therefore, for a patient with presence of MAHE, time (months) to first occurrence of a MAHE will be the minimum among the 5 potentially derived durations (i.e. calculated as (date of first occurrence of a MAHE component event – date of randomization + 1)/30). A patient without any MAHE will be censored at the end of the last cycle (i.e. last cycle of placebo or trilaciclib), death, end of study, or date of last contact, whichever is earlier.

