6.2.7.1.2 Key Secondary Efficacy Analyses

Occurrence of RBC transfusions on/after 5 weeks on study is a binary variable and will be summarized using the same method for occurrence of SVN described in [Section 6.2.7.1.1](#) except baseline HGB will be used as a covariate instead of baseline ANC in the modified Poisson model. Also, the offset will be the logarithm transformation of duration of induction treatment period divided by 7 (i.e. week) instead of number of induction cycles, and. An additional sensitivity analysis will look all transfusions during the induction treatment period, and all transfusions with a subset of subjects completing at least 1 cycle.

Occurrence of GCSF administration is a binary variable and will be summarized using the same method for occurrence of SVN described in [Section 6.2.7.1.1](#).

All-cause dose reductions will be analyzed to compare trilaciclib and placebo using a negative binomial regression model to account for the potential over-dispersion. The model includes the stratification factors of ECOG (0 or 1 vs. 2) and brain metastases (Yes vs. No), and treatment as a fixed effect. The logarithm transformation of number of induction cycles will be included as an offset variable in the modeling. The two-sided p-value, aRR (trilaciclib vs placebo) and its 95% CIs will be presented.

The total number of all-cause dose reductions will be summarized descriptively, along with the number of induction cycles, and the event rate per cycle (calculated as the total number of events/total number of induction cycles). The cumulative incidence of events during the induction treatment period will be summarized and presented graphically by cycle.

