6.2.7.2 Supportive Secondary Efficacy Analyses

6.2.7.2.1 Analyses of Total Number of MAHE

The total number of MAHE in [Section 5.1.3.1](#) will be analyzed to compare trilaciclib and placebo using a negative binomial regression model to account for the potential over-dispersion. The model includes the stratification factors of ECOG (0 or 1 vs. 2) and brain metastases (Yes vs. No), and treatment as a fixed effect. The logarithm transformation of duration of induction treatment period divided by 7 (i.e. week) will be included as an offset variable in the modeling. The two-sided p-value, aRR (trilaciclib vs placebo) and its 95% CIs will be presented.

The total number of MAHE will be summarized descriptively, along with the weeks of induction treatment duration, and the event rate per week (calculated as the total number of events/duration of induction treatment period divided by 7 [i.e. week]). The cumulative incidence of events during the induction treatment period will be summarized and presented graphically in three-week intervals.

The total number of individual MAHE components (specified in [Table 4](#)) will be summarized similarly, except that DSN > 5 days will be summarized cumulatively by cycle instead of three week intervals, and the offset will be the logarithm transformation of number of induction cycles divided instead of duration of induction treatment period.

Time-to-first MAHE endpoints (overall and individually) in [Section 5.1.3.1](#) will be summarized similar to DSN, Strategy 2 as described in [Section 6.2.7.1.5](#). A graphical display of cumulative incidence will also be presented.

An event chart of the induction treatment period will also be included, with horizontal bars for each subject's cycle length and time on the x-axis, with points plotted for each of the MAHE components.

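### The induction treatment period is not cut at death, consent withdrawal or loss to follow-up, so weekly offsets and rates count up to five weeks per affected patient as event-free time at risk

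*SAP*

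**What the plan says.** SAP section 5 opens its table of terms with "The following general definitions will be applied to all endpoints derivation unless otherwise specified". The induction treatment period is "Between the date of randomization and end of cycle for the last Induction cycle". The end of a cycle is normally Day 1 of the next one, but "For the last induction cycle (where no subsequent maintenance cycle is given), the end of cycle will be defined as Day 36", counted from that cycle's first dose. Neither definition has an exception for death, withdrawal or loss to follow-up. Protocol section 13.5 describes the same period, also without a cut.

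The length of this period enters the analysis in these places:

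- RBC transfusions on or after Week 5 (SAP 6.2.7.1.2; H4 in Family 3 of the multiplicity procedure): "the offset will be the logarithm transformation of duration of induction treatment period divided by 7".
- Total MAHE (SAP 6.2.7.2.1): "The logarithm transformation of duration of induction treatment period divided by 7 (i.e. week) will be included as an offset variable". The same duration is the denominator of the weekly MAHE rate, and the individual components other than prolonged severe neutropenia follow the same approach.
- IV antibiotics, infection SAEs and pulmonary infection SAEs (SAP 6.2.7.2.5): the same weekly offset.

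Elsewhere the SAP does stop the clock. Time to first MAHE (SAP 5.1.3.1) is censored at the end of the last cycle, "death, end of study, or date of last contact, whichever is earlier". Under DSN Strategy 1 (SAP 5.1.1.2.1), an unresolved episode ends at death, or at the last ANC after withdrawal or loss. These rules are specific to those endpoints. Duration of exposure (SAP 5.2.1.1) is a separate quantity used only in exposure summaries, so it does not supply the missing cut.

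**The concern.** An offset should measure time in which an event could occur and be recorded. After death none can occur; after withdrawal or loss none is recorded. Counting that time as exposure lowers the weekly rate, and lowers it more in the arm that loses more patients. The rate ratio then shifts in favour of that arm.

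The SAP is also inconsistent with itself. A patient who dies on Cycle 1 Day 10 without a MAHE is followed to Day 10 in the time-to-first-MAHE analysis and to Day 36 in the total-MAHE analysis that it is meant to support.

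**Working it through.** The plan states no figure for this point, so there is nothing to reproduce. The check is arithmetic on the definitions.

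**Maximum per patient.** Take Day 1 as the first dose of the last cycle. Excess = 36 − exit day. The largest value is 36 − 1 = 35 days = 5.0 weeks.

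**Examples.** Assume randomization 2 days before dosing (Protocol 10.2 allows up to 3) and undelayed 21-day cycles. For exit on day *d* of last cycle *c*, observed days = 2 + 21(*c* − 1) + *d*, and counted days = 2 + 21(*c* − 1) + 36.

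| Exit | Observed weeks | Counted weeks | Ratio |
|---|---|---|---|
| Cycle 1 Day 5 | 7/7 = 1.0 | 38/7 = 5.4 | 5.4 |
| Cycle 1 Day 10 | 12/7 = 1.7 | 5.4 | 3.2 |
| Cycle 1 Day 15 | 17/7 = 2.4 | 5.4 | 2.2 |
| Cycle 1 Day 20 | 22/7 = 3.1 | 5.4 | 1.7 |
| Cycle 4 Day 8 | 73/7 = 10.4 | 101/7 = 14.4 | 1.4 |

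The Cycle 1 ratios apply to MAHE, IV antibiotics and the infection SAE endpoints only.

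**H4 separately.** Only transfusions from Week 5 (35 days after randomization) count. A Cycle 1 exit has no H4 time at risk under either rule, and the uncut period runs only 38 − 35 = 3 days past Week 5. Later exits matter more:

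- Cycle 2 Day 8: observed to day 31, counted to day 59, so 59 − 35 = 24 spurious days after Week 5.
- Cycle 3 Day 8: observed to day 52, counted to day 80, so 28 spurious days.

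**Arm level.** The documents give no rate of death, withdrawal or loss during induction, so these rates are assumed. Take 53 patients per arm (106/2), exits spread evenly over cycles and days, and all others completing four undelayed cycles. Simulated arm totals (20,000 replicates):

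| Exits | Counted weeks | Observed weeks | Excess | Rate understated |
|---|---|---|---|---|
| 5% | 652.1 | 642.8 | 9.3/642.8 = 1.4% | 9.3/652.1 = 1.4% |
| 10% | 645.5 | 626.9 | 18.6/626.9 = 3.0% | 18.6/645.5 = 2.9% |
| 15% | 638.8 | 610.8 | 28.0/610.8 = 4.6% | 28.0/638.8 = 4.4% |

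Hand check at 5%: a mean excess of about 25 days (3.6 weeks) over 642.8/53 = 12.1 observed weeks gives 0.05 × 3.6/12.1 = 1.5%.

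Rate ratio with 5% exits in one arm and 15% in the other: (638.8/610.8)/(652.1/642.8) = 1.031. The ratio of trilaciclib to placebo is multiplied by 1/1.031 = 0.970 if trilaciclib loses more, and by 1.031 if placebo does.

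**Wider range.** Understatement = 1 − T/(T + f·x), with T = 12.5 observed weeks per patient (assumed), f the share affected and x the mean excess weeks.

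- f = 2%, x = 2: 1 − 12.5/12.54 = 0.3%.
- f = 20%, x = 5: 1 − 12.5/13.5 = 7.4%.
- 20% trilaciclib against 5% placebo, x = 4: ratio factor 12.7/13.3 = 0.955; reversed, 1.047.
- Equal f and x in both arms: factor 1.00.

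**The case against.** The case against acting rests on scope, size and planned checks.

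- **Scope.** Occurrence of severe neutropenia, G-CSF and the key secondary dose-reduction model use number of induction cycles as offset; DSN uses none. Apart from H4, the affected endpoints are supportive in this SAP. Patients who start maintenance are unaffected, because their last induction cycle ends on maintenance Day 1. This stands.
- **Stopping treatment is not loss of observation.** AEs and concomitant medications, including blood products, are collected for 30 days after the last dose (Protocol 8.6 and 11.4.1.7). From a Day 3 dose that reaches Day 33, and the +3-day visit window reaches Day 36. So Day 36 is a sensible endpoint for someone still followed. This stands, and confines the problem to death, consent withdrawal and loss to follow-up.
- **Planned checks.** For RBC transfusions, SAP 5.1.3.1 and 6.2.7.1.2 plan analyses excluding patients who do not start a second cycle or complete a first. SAP 6.2.7.1.5 plans CMH analyses, with death counted as an event, a worst-comparison analysis and a tipping-point analysis for binary endpoints. Time to first MAHE is censored correctly. These partly test the conclusions; none corrects the person-time in the Poisson or negative binomial models.
- **Size.** Using the transfusion proportions from G1T28-02 (Protocol 4.3.1: 21.6% and 5.7%) with 53 per arm, expected events are 11.4 and 3.0, and SE(log RR) ≈ √(0.784/11.4 + 0.943/3.0) = 0.62. A shift of ln 1.031 = 0.03 is about 0.05 standard errors. This stands as an illustration.

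A reader might infer that H4 exposure is overstated up to fivefold. It is not: the large ratios come from Cycle 1 exits, who have no H4 time at risk under either rule.

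**Conclusion.** The definition gives wrong person-time for patients who die, withdraw consent or are lost before Day 36 of a last induction cycle with no maintenance after it. It conflicts with the rule for time to first MAHE. The error is at most 5.0 weeks per affected patient. At assumed exit rates of 5% to 15%, weekly rates are understated by about 1% to 5%. The rate ratio moves by about 3% for exits of 5% against 15%, and stays about unchanged when exits are equal.

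These arm-level figures rest on assumed exit rates, evenly spread exits and crude ratios of arm totals; the covariate-adjusted models would differ somewhat. For H4 the distortion comes mainly from exits after Cycle 1.

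Two stronger readings are not supported. The primary conclusions are not at risk, because neither primary analysis uses this duration. Nor does the rule favour trilaciclib as such: the direction depends on which arm loses more patients, and the documents do not say. The change is worth making because the error is systematic, reaches one multiplicity-controlled hypothesis and is easily avoided.

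**What to change.** Add one sentence to SAP section 5: for event counting, the weekly offset and weekly rates, the induction treatment period ends at the earliest of the end of the last induction cycle, death, withdrawal of consent, end of study or last contact. This extends the time-to-first-MAHE rule in SAP 5.1.3.1. Consent withdrawal should be named, because monthly survival contact (Protocol 10.7) can continue after event collection has ended, so last contact alone may be too late.

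For H4 the change removes the time after exit. It does not remove the first five weeks from the offset, in which no qualifying transfusion can occur.

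The cost is one sentence and a small change to one derived variable, made before unblinding. The dates needed are already collected.

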5.1. Efficacy Endpoints

Unless otherwise specified, all primary and key secondary efficacy endpoints will be evaluated and derived for the induction treatment period.

5.1.1. Primary Endpoints

5.1.1.1. Occurrence of Severe (Grade 4) Neutropenia

For the induction treatment period, the total number of SVN events is the number of induction cycles where at least one ANC value is $< 0.5 \times 10^9/L$. For example, if Cycle 2 has two ANC values that are both $< 0.5 \times 10^9/L$, this only counts as one event. If a patient did not have any SVN events, the value of 0 will be assigned to that patient. The number of induction cycles without SVN is calculated as total number of induction cycles received – total number of induction cycles with SVN. Unscheduled data and the actual assessment date (rather than visit date) will be included in the derivation.

Therefore, any occurrence of an SVN during an induction cycle or the induction treatment period is defined as a binary variable (Yes or No); Yes, if total number of induction cycles with SVN ≥ 1 is observed, No for other scenarios.

5.1.1.2. Duration of Severe (Grade 4) Neutropenia (DSN)

There will be three different strategies for assessing DSN in each cycle. All strategies will be applied to derive the DSN, with strategy 1 considered as the primary, and strategy 2 and strategy 3 being supportive sensitivity analyses. The DSN in Cycle 1 is considered for this primary endpoint. Any unscheduled data and the actual assessment date (rather than visit date) will be included in the derivation of each strategy.

5.1.1.2.1 Strategy 1: Without Imputation of Missing ANC Values

Within each cycle, the DSN (days) is defined as the number of days from the date of first ANC value of $< 0.5 \times 10^9/L$ observed between start of cycle and end of cycle, to the date of first ANC value $\geq 0.5 \times 10^9/L$ that meets the following criteria: (1) occurs after the ANC value of $< 0.5 \times 10^9/L$ and (2) no other ANC values $< 0.5 \times 10^9/L$ occur between this day and end of cycle. DSN is set to 0 in patients who did not experience SVN in a cycle. Any unscheduled data and the actual assessment date (rather than visit date) will be included in the derivation. The following rules will be applied in the calculation:

- For a cycle where the SVN event does not resolve by end of the cycle, DSN will be assigned as above except the end date will be the end of cycle.
- For a cycle where the patient dies during the SVN event, DSN will be assigned as above except the end date will be the date of death.
- For a cycle where the patient withdraws consent or is lost to follow-up during the SVN event, DSN will be assigned as above except the end date will be the date of the last ANC assessment prior to the end of study.

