5.1.1.2.2 Strategy 2: Without Imputation, Censoring Unresolved SVN

Within each cycle, DSN (days) is defined as the number of days from the date of first ANC value of $<0.5 \times 10^9/L$ observed between start of cycle and end of cycle, to the date of first ANC value $\geq 0.5 \times 10^9/L$ that meets the following criteria: (1) occurs after the ANC value of $<0.5 \times 10^9/L$ and (2) no other ANC values $<0.5 \times 10^9/L$ occur between this day and end of cycle. If no SVN occurs, then the cycle is not used in this analysis. The following censoring rules will be applied in the calculation:

- For a cycle where the SVN event does not resolve by end of the cycle, DSN will be assigned as above except the end date will be the earlier of end of cycle or date of last contact.
- For a cycle where the patient dies, withdraws consent, or is lost to follow-up during the SVN event, DSN will be assigned as above except the end date will be the date of the last ANC assessment prior to the end of study.

For the induction treatment period, the overall DSN (days) is the median value among the DSN (days) from all cycles. The following data handling conventions will apply:

- For those patients where all event duration values are derived from cycles with censored data, the median value for that patient will be the median censored value. It will be considered a censored value;
- For those patients where a subset of event duration values are derived from cycles with censored data, the median value for that patient will be estimated using the Kaplan-Meier method. It will be considered as an observed value (i.e. no censored value);
- For those patients where the median event duration cannot be derived (e.g. ≤ 2 values), the longest event duration amongst all the cycles will be used regardless of censoring, but the corresponding censoring flag will be carried over for analysis.

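### A patient lost after a single Grade 4 count scores 0 days on the primary DSN endpoint, the same as a patient with no severe neutropenia

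*SAP*

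**What the plan says.** SAP 5.1.1.2 sets out three ways of deriving DSN, "with strategy 1 considered as the primary, and strategy 2 and strategy 3 being supportive sensitivity analyses". It adds: "The DSN in Cycle 1 is considered for this primary endpoint".

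Strategy 1 (SAP 5.1.1.2.1) counts days from the first ANC below 0.5 × 10⁹/L to the first lasting recovery in the cycle. The other cases are:

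- No severe neutropenia: "DSN is set to 0 in patients who did not experience SVN in a cycle".
- Not resolved by the end of the cycle: "DSN will be assigned as above except the end date will be the end of cycle".
- Death during the episode: "DSN will be assigned as above except the end date will be the date of death".
- Withdrawal of consent or loss to follow-up during the episode: "the end date will be the date of the last ANC assessment prior to the end of study".

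SAP 5.1.1.1 makes occurrence a Yes if any induction cycle has at least one ANC below 0.5 × 10⁹/L. SAP 6.2.7.1.4 makes Cycle 1 DSN hypothesis H1. H2 (occurrence) is tested only if H1 is significant, and H3 to H5 only if H2 is.

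**The concern.** The lowest possible score should mean that no severe neutropenia was seen. Under the withdrawal rule it can also mean that severe neutropenia was seen once and the patient then disappeared. The two co-primary endpoints then contradict each other for that patient: neutropenic for occurrence, not neutropenic for duration.

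The pattern is plausible because counts are sparse. After Day 3, scheduled hematology in a cycle falls only on Days 8 and 15 (SAP Table 2). A patient with a low Day 8 count who leaves before Day 15 has exactly one Grade 4 value.

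The score matters because H1 gates every other test in this SAP. It also feeds the prolonged-neutropenia component of MAHE (more than 5 days), which SAP Table 4 derives from Strategy 1. A lost patient scored 0 is not counted there.

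**Working it through.** **The plan's own figure.** SAP 2.3 assumes a 2-day difference, SD 2.5, one-sided 0.0125 and 90% power. A two-sample t-test with noncentral t gives power 0.899 at 40 per arm and 0.907 at 41, so 41 per arm, 82 in total, as stated. Dividing by the 95% evaluability rate, 41/0.95 = 43.2, rounded up to 44 per arm, gives the stated 88. The final size is 106, or 53 per arm.

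**Day count.** DSN is worded as days from one date to another with no added day. SAP Section 5 does add 1 when it defines cycle duration. So DSN = end date − date of first Grade 4 count. For a first Grade 4 count on Cycle 1 Day 8:

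| Course | Calculation | DSN (days) |
|---|---|---|
| No severe neutropenia | set by rule | 0 |
| Lost, no further ANC | 8 − 8 | 0 |
| Lost after a second Grade 4 count on Day 15 | 15 − 8 | 7 |
| Recovered on Day 15 | 15 − 8 | 7 |
| Unresolved, Cycle 2 starts on Day 22 | 22 − 8 | 14 |
| Unresolved, no later cycle (end of cycle Day 36, SAP Section 5) | 36 − 8 | 28 |
| Death on Day 9, 14 or 20 | 9 − 8, 14 − 8, 20 − 8 | 1, 6, 12 |

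**Size in days.** Suppose 1, 2 or 3 of 53 placebo patients score 0 instead of 7. The placebo mean falls by 7/53 = 0.13, 14/53 = 0.26 or 21/53 = 0.40 days. With SD 2.5, 53 per arm and one-sided 0.0125, t-test power falls from 0.966 to 0.941, 0.903 or 0.845. This puts every loss in the placebo arm.

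**Size by ranks.** One-sided Wilcoxon test at 0.025, 53 per arm, DSN 7 days (14 in 10% of neutropenic patients). The Cycle 1 rates are assumptions, and ranges cover repeated runs of 1,500 to 4,000 trials.

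- 30% neutropenia in both arms, loss applied to 6%, 10% or 15% of neutropenic patients in both arms: rejection 2.0% to 2.8%, so no inflation.
- The same rates, but 1, 2 or 3 trilaciclib patients forced to 0 and no placebo patient: about 4%, 7% and 10%. With the two patients scored 1 day instead, rejection returns to about 3% to 4%.
- 30% versus 10%, loss in 5% to 10% of neutropenic patients in both arms: power falls from about 75% to about 72% to 68%.
- 30% versus 10%, 2 placebo patients forced to 0: 57% to 59%.
- 40% versus 8%, 2 placebo patients forced to 0: 98% to about 95%.

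The planned test is a nonparametric ANCOVA. The SAP does not say whether ranks or days enter it, so both sets of figures are stand-ins.

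**Strategy 2 (secondary).** It summarizes over neutropenic cycles by the median, but when that cannot be derived (2 or fewer values), "the longest event duration amongst all the cycles will be used regardless of censoring". Durations 7 and 14 score 14; durations 7, 7 and 14 score 7. A further neutropenic cycle lowers the score.

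**The case against.** The strongest case is that the plan already checks this and that few patients can trigger it.

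- Strategy 3 (SAP 5.1.1.2.3, rule 5) sets every day from the last assessment to end of cycle as neutropenic when an episode does not resolve, with no exception for loss. SAP 6.2.7.1.5 repeats the primary DSN analysis on it. This stands. A reader who notes that the death, worst-comparison and tipping-point analyses are confined to binary endpoints might infer that DSN has no protection against loss. For loss that is wrong; for death Strategy 3 also stops at the date of death.
- Protocol 6.1.1 and 10.8 ask patients who stop drug to finish the cycle's assessments, and unscheduled counts are used. Only full withdrawal or loss before another count triggers the 0. This stands, and limits the number.
- Counting both end dates would give 1 day rather than 0. The SAP does not say so, and the wording for DSN reads as subtraction.
- Extending the end-of-cycle rule to losses in the primary analysis looks like the natural remedy. It is harsh: with no later cycle, one Day 8 count becomes 28 days. Three such patients scored 28 rather than 7 would move an arm mean by 3 × 21/53 = 1.2 days, against a design difference of 2.
- Ending duration at death is a defensible while-alive definition. A reader might infer that death always scores better than survival. It does not: death on Day 20 scores 12, recovery on Day 15 scores 7. Worst rank is a choice on which statisticians differ.

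**Conclusion.** The withdrawal rule gives a wrong score in one identifiable case: an observed Grade 4 patient is tied with patients who had none, on the endpoint that gates all others. It should be corrected, though the likely effect is small. The documents give no count of affected patients; 0 to 3 is an assumption. With losses spread over both arms the result is a modest loss of power.

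A reader might infer from the 7% and 10% figures that H1 does not control its error rate. Those figures put every loss in the trilaciclib arm in every simulated trial, and nothing in the documents suggests that imbalance. If the drug works, more placebo patients are neutropenic and exposed to the 0 score, which works against the claim.

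The Strategy 2 inconsistency is real but confined to an induction-wide supportive analysis. It does not touch H1.

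**What to change.** Before unblinding, amend SAP 5.1.1.2.1 to:

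1. State the day-count convention.
2. Set a minimum of 1 day for any cycle with an observed ANC below 0.5 × 10⁹/L. A floor is better than adding 1 to every duration: where the end date is the first recovered count, adding 1 would count that day and turn a 5-day episode into 6, past the more-than-5-days threshold.

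Keep the Strategy 3 repeat as the sensitivity analysis for losses, and note that it uses Day 36 when no later cycle is given. The floor does not alter the MAHE component, since 1 day is still not more than 5.

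Optionally, add one sensitivity analysis that ranks death during an episode as worst, because the planned death analysis covers only binary endpoints. In Strategy 2, use one summary rule whatever the number of neutropenic cycles.

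The cost is a few words of SAP text and a few lines of code. The only downside is a slightly less favourable score for the few patients who leave.
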